## 9 Patient Accounting and Disposition

### 9.1 *Patient accounting*

The number and relative frequencies of subjects in each Cohort will be presented overall, by Analysis Sets, and individual Cohorts (i.e., Cohorts: A, A1, A2, A3, A4, A5, A6, B, B1, and B2 ), including individual reasons of exclusion from the respective analysis set.

A list of subjects' first ALM-488 infusion date time start, date time end, time to discontinuation and reasons for discontinuation will be presented.

### 9.2 *Disposition and withdrawals*

The number and relative frequency will be presented for

- Subjects completing the study
- Subjects who prematurely discontinued the study
- Reasons for study discontinuation (Adverse Event, death, lost to follow-up, physician decision, pregnancy, progressive disease, site or study terminated by sponsor, technical problems, withdrawal by subject, adverse device effect or other)
- Subjects completing surgery
- Subjects completing treatment

Completing the study is defined as having completed the infusion, surgery, and end of study telephone call.

A list of subjects' trial end date, time to trial discontinuation and reason for trial discontinuation will be created.

### 9.3 *Minor and Major Protocol deviations*

The number and relative frequency of subjects with major protocol deviations will be presented by treatment cohort and study site for FAS.

Listings of all subjects with protocol deviations as specified above violating in- and exclusion criteria and allocation to trial populations will be created.

## 10 Demographics and Baseline Characteristics

Demographic and baseline characteristics as specified in detail below will be presented descriptively overall, by Analysis Sets, and by individual Cohorts (i.e., Cohorts: A, A1, A2, A3, A4, A5, A6, B, B1, B2).

### 10.1 *Demographics*

QMS Document Name: Statistical Analysis Plan	Page 16 of 29
QMS No (include version ref): STF-015-GL.02	Document date: 09JUL2019
CONFIDENTIAL	

The following demographic characteristics will be presented by individual Cohorts (i.e., Cohorts: A, A1, A2, A3, A4, A5, A6, B, B1, B2).

- Sex (male/female)
- Age (years)
- Age group ( $\geq 18$  and  $< 65$ ,  $\geq 65$  and  $< 85$ ,  $\geq 85$  years)
- Race (American Indian or Alaska Native, Asian, Black or African American, Native Hawaiian or Other Pacific Islander, White, Unknown, Other)
- Ethnicity (Hispanic or Latino, Not Hispanic or Latino, Not Reported, Unknown)
- Childbearing potential or less than 2 years menopausal (yes/no);
- Acceptable contraception (yes/no)
- Surgery type (Thyroidectomy, Parotidectomy, Neck Dissection)

Date of informed consent, protocol version, informed consent form (ICF) type and ICF version number will be listed.

### **10.2 Surgery Type**

The type of surgery (Thyroidectomy, Parotidectomy, Neck Dissection) will be summarized overall in the Demographics and Baseline Characteristics and further listed overall, and by individual Cohorts (i.e., Cohorts: A, A1, A2, A3, A4, A5, A6, B, B1, B2).

### **10.3 Medical history**

The diseases are coded according to the latest available Medical Dictionary for Regulatory Activities (MedDRA® version 23.1). The frequency of diseases recorded from medical history will be presented after classification into previous and concomitant conditions by system organ class (SOC) as well as the frequencies of preferred terms (PT) within each SOC. If subjects have more than one disease within an SOC or PT they will be counted only once for the respective SOC or PT.

A listing of medical history will be provided.

### **10.4 Exposure and Compliance**

The number and percentage of subjects will be presented by individual Cohorts (i.e., Cohorts: A, A1, A2, A3, A4, A5, A6, B, B1, B2) on the SAF analysis set.

The infusion duration will be calculated in minutes as:

When there are no interruptions in infusions:

Infusion duration (minutes) = (time of infusion end – time of infusion start) + 1

When infusion interruptions will be reported the time of the interruption need to be subtracted from time of infusion.

Descriptive statistics for the treatment duration will be presented.

QMS Document Name: Statistical Analysis Plan	Page 17 of 29
QMS No (include version ref): STF-015-GL.02	Document date: 09JUL2019
CONFIDENTIAL	

The infusion completed per protocol, details if deviated as well as infusion reactions IR will be described.

Study ALM-488 dose and timing of administration and the summary of exposure will be listed by individual Cohorts (i.e., Cohorts: A, A1, A2, A3, A4, A5, A6, B, B1, B2) for the SAF Analysis Set

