### **8.7 Study Day, Visit Window, and COVID-19**

For each patient, the day of surgery will be considered Study Day 1. Each assessment will be assigned a study day. The calculation for study day is dependent on whether the actual date of assessment is before or after the date of study Day 1 and is calculated as follows:

Before study Day 1:

study day = (date of assessment – Date of first dose of study medication Day 1).

On or after study Day 1:

study day = (date of assessment – Date of first dose of study medication Day 1) +1.

Days within the screening period will be numbered with negative numbers until day -1 defined as the day before AML-488 treatment (Day 1).

If the full date of the assessment is not known or not imputable based on the guidelines in Section 7.3, then no study day will be assigned. Study Day, and any corresponding durations will appear partial or missing in the listings.

For each patient, the end of the study is defined as the date of their last contact in this study.

Data will be analyzed based on the categorized visit captured in the database. No dates will be used to reassign visits or define visit windows. Although Day 15 or Early Termination is defined with +/-8 days, extensions to the visit window may be allowed due to impacts related COVID-19. Although Day 28/End of Study is defined with +/- 5 days, extensions to the visit window may be allowed due to impacts related COVID-19.

Any impacts due to COVID-19 will be noted in the study documentation.

The visits captured in the database include:

- Screening (Day -28 to Day -1)
- Baseline (Day 1) (pre- and post-operative)
- Day 15 or Early Termination

QMS Document Name: Statistical Analysis Plan	Page 15 of 29
QMS No (include version ref): STF-015-GL.02	Document date: 09JUL2019
CONFIDENTIAL	

- Day 28/End of Study

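### The SAP's formula for uninterrupted infusions adds 1 minute to a difference of clock times, so the descriptive exposure results overstate duration by about a minute

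*SAP*

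**What the plan says.** Section 10.4 of the SAP (Exposure and Compliance) sets the unit first: "The infusion duration will be calculated in minutes as" the expression that follows. That expression is introduced by the condition "When there are no interruptions in infusions" and reads "Infusion duration (minutes) = (time of infusion end – time of infusion start) + 1".

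Interrupted infusions get one sentence and no formula: "When infusion interruptions will be reported the time of the interruption need to be subtracted from time of infusion". It does not say whether the added minute is kept, or how the length of a gap is to be counted.

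The section states how the result is used: "Descriptive statistics for the treatment duration will be presented". The outputs are Table 14.1.9 (Cohorts A and B) and Listing 16.2.7, all on the Safety Analysis Set.

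Two other places bear on the point. Section 9.1 plans a list by subject that includes "first ALM-488 infusion date time start, date time end", so start and end are held as date-times and not only as dates. Section 8.7 has the SAP's other added 1, in the study-day rule: "study day = (date of assessment – Date of first dose of study medication Day 1) +1".

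**The concern.** Study days are labels on whole calendar days. With the dosing day numbered 1, an assessment on that same date must come out as Day 1, so adding 1 to the date difference is correct. Infusion start and end are points on a clock, and the time between two points is their difference. An infusion running from 08:00 to 08:10 lasts 10 minutes; section 10.4 would report 11. One whose recorded end equals its recorded start would be reported as 1 minute.

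The SAP gives no reason for the extra minute. It looks like the day-count convention carried over to minutes. What is at stake is modest: the exposure outputs would show durations about a minute too long, and these would disagree with the start and end times listed for the same subjects.

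**Working it through.** **Inputs.** The formula, its unit and its restriction to uninterrupted infusions come from SAP 10.4. Start and end as date-times come from SAP 9.1. The planned infusion length is not in the supplied documents, so the lengths below are assumptions that show a range. The SAP states no numeric duration, so there is no figure of its own to reproduce.

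**Step 1: uninterrupted infusions.** Let S be the start and E the end, in minutes. Elapsed time is E − S and the SAP value is (E − S) + 1. The excess is (E − S + 1) − (E − S) = 1 minute whatever S and E are. The relative excess is 1/(E − S).

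| Assumed length (min) | SAP value (min) | Excess (min) | Relative excess |
|---|---|---|---|
| 5 | 6 | 1 | 1/5 = 20.0% |
| 10 | 11 | 1 | 1/10 = 10.0% |
| 15 | 16 | 1 | 1/15 = 6.7% |
| 30 | 31 | 1 | 1/30 = 3.3% |
| 60 | 61 | 1 | 1/60 = 1.7% |

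**Step 2: could the extra minute correct for times recorded to the whole minute?** Suppose both times are truncated to the minute. The recorded difference then differs from the true one by (fraction of a minute dropped from S) − (fraction dropped from E). Each fraction lies between 0 and 1. If both have the same distribution, the error averages 0 and lies between −1 and +1. Adding 1 moves the average to +1 and the range to 0 to +2. A simulation of 400,000 infusions around each of 5, 10, 30 and 60 minutes, with times truncated or rounded, agreed:

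| Rule | Mean error (min) | Range of error (min) |
|---|---|---|
| E − S | 0.00 | −1 to +1 |
| (E − S) + 1 | +1.00 | 0 to +2 |

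The plain difference is unbiased, and the added minute introduces a bias.

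**Step 3: interrupted infusions.** Take start at 0, stop at 10, resume at 15 and end at 35 minutes. True infusion time is 10 + 20 = 30 minutes. The SAP wording can be programmed in four ways:

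- formula kept, gap as a plain difference: (35 + 1) − 5 = 31;
- extra minute dropped: 35 − 5 = 30;
- extra minute applied to the gap as well: (35 + 1) − (5 + 1) = 30;
- extra minute applied to each running segment: (10 + 1) + (20 + 1) = 32.

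The first is the natural reading and has the same 1-minute excess. The text does not exclude the others.

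**Step 4: effect on the planned statistics.** SAP 8.1 summarises continuous variables by mean, standard deviation, minimum, quartiles, median and maximum. Adding a constant c = 1 to every value raises each location statistic by 1. It leaves the standard deviation unchanged, and it cancels in a difference between cohorts: (mean₁ + 1) − (mean₂ + 1) = mean₁ − mean₂. If interrupted infusions were programmed differently from uninterrupted ones, the shift would no longer be constant, though in the example above it stays between 0 and 2 minutes.

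**The case against.** The case on the other side does not defend the formula; it concerns reach and consequence, and most of it stands.

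- **Not shown for every subject.** A reader might infer that each reported duration is exactly 1 minute too long. The formula is written for uninterrupted infusions only, and Step 3 shows that the interrupted case is open. With whole-minute recording, 1 minute is an average, and a single infusion may be off by 0 to 2 minutes.
- **Not a safety endpoint.** A reader might infer that the error reaches the primary safety objective. SAP 7.1 lists adverse events, vital signs, laboratory evaluations, ECGs and physical examinations. Duration is not among them. The dose-limiting toxicity rule and the choice of Optimal Dose (SAP 4.1 and 12) do not use it either.
- **No planned rate or target comparison.** A reader might infer that infusion rates, or a comparison with a planned length, would be distorted. The supplied text plans neither. Section 10.4 does report whether the infusion was completed per protocol, but does not tie that to the formula. Pharmacokinetic methods are in a separate SAP, so nothing can be claimed about them. The timing analyses use time from injection to skin incision.
- **Recoverable.** Because start and end date-times are to be listed, a reader can recompute elapsed time.

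A further defence is that the extra minute is a deliberate inclusive convention, giving a nonzero value to anyone who received drug. The SAP does not say so. With times truncated to the minute, such a count gives the number of clock minutes touched by the infusion, which is not its duration. The extra minute would remove a bias only if starts were rounded up and ends rounded down, and the SAP states no such recording rule. This defence does not stand.

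**Conclusion.** The formula is wrong as written, with a small effect. For uninterrupted infusions it overstates elapsed time by 1 minute, on average if times are recorded to the whole minute. For interrupted infusions the rule is incomplete, and on the natural reading it carries the same excess.

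The consequence is limited to the descriptive exposure summary and listing, where location statistics move up by about 1 minute. Standard deviations, between-cohort differences, safety endpoints and dose-limiting toxicity decisions are unaffected. The first two hold provided the same minute is added to every infusion.

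Two assumptions remain. The relative sizes, 20% down to 1.7%, depend on assumed lengths of 5 to 60 minutes; only the absolute minute follows from the documents. And the treatment duration that section 10.4 says will be summarised is taken to be the infusion duration it has just defined. This is a correction of the lowest severity.

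**What to change.** In SAP 10.4, delete the added 1 and give one definition for all infusions:

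duration (minutes) = (end − start) − Σ(resume − stop),

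with the sum over reported interruptions and equal to 0 when there are none. Compute it from the date-times, so that an infusion crossing midnight is handled correctly. The worked example then gives (35 − 0) − (15 − 10) = 30 minutes, with no choice left to the programmer.

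The study-day rule in SAP 8.7 should stay as it is.

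The cost is one line of SAP text and the matching line in the program for Table 14.1.9 and Listing 16.2.7. No new data, additional analysis or clinical judgement is needed.

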#### **10.5 Dosage and Timing of Administration**

Descriptive statistics for the dose and timing will be presented overall and by individual Cohorts (i.e., Cohorts: A, A1, A2, A3, A4, A5, A6, B, B1, B2) for the SAF Analysis Set.

#### **11 Previous and Concomitant Therapies**

Previous and concomitant medications are coded according to the World Health Organization drug dictionary (WHO-Drug version B3 March 2020) and stored with Anatomical Therapeutic Class (ATC) codes and generic names.

Therapies will be classified as previous if the stop date and/or time was before the date of first dose of study medication. All other medications are defined as concomitant. Missing or partly missing stop dates will be imputed using the rules defined in Section 7.3.

The number and frequency of previous and concomitant medications will be given per ATC level 2. If a patient has received more than 1 drug within an ATC class, he/she will be counted only once for this ATC class.

Previous and Concomitant Therapies will be listed overall, by Analysis Sets, and by individual Cohorts (i.e., Cohorts: A, A1, A2, A3, A4, A5, A6, B, B1, B2).

#### **12 Determination of Optimal Dose**

The optimal dose will be the lowest possible dose and toxicity profile that achieves adequate imaging performance: (1) DLT rate is 0 subjects for a 3-patient cohort (2) adequate fluorescence signal of nerves compared to background non-nerve tissue. A dot plot will be presented to display Cohorts A1 through A6. Cohorts A1 through A6 will be displayed on the x-axis, with a cluster of 3 to 6 dots for each cohort. The dose will be displayed on the y-axis. Dots will be open circles for subjects who do not experience a DLT. Solid red dots will be used for subjects who experience a DLT. A listing of the DLTs will also be provided.

Image intensity ratios will also be plotted with time from injection to skin incision on the x-axis, image intensity ratio on the y-axis, and a separate color for each dose level.

#### **13 Efficacy**

The data on the signal-to-background ratio for FL and WLR will be provided by Stanford University for the different regions of interest ROIs. All efficacy analyses will be completed on the FAS Analysis Set and will be repeated in PP analysis set if the latest is different from FAS Analysis Set. The analyses using signal to background ratio SBR for cohort A will only use images produced by Zeiss camera while both Zeiss and OnLume devices will be used for timing cohort B.

QMS Document Name: Statistical Analysis Plan	Page 18 of 29
QMS No (include version ref): STF-015-GL.02	Document date: 09JUL2019
CONFIDENTIAL	

### **13.1 Timing, Dose, Size and Intensity**

The efficacy endpoints pertaining to timing of administration, dose, and intensity (signal-to-background ratio SBR), along with the surgeon rating scale will be assessed throughout enrollment into Cohorts A1-A6 to determine the final dose for use in Cohorts B1 and B2. These efficacy endpoints will also be used to evaluate the effect of timing of administration of ALM-488 by comparison of Cohort B1 and B2. The following analyses are planned for these efficacy endpoints:

- For each Cohort, SBR will be averaged to get a single mean ratio per patient; then a paired t-test or Wilcoxon signed rank test will be used, as appropriate, to compare SBR between FL and WLR.
- SBR will be also listed by cohort type, and surgery type and device for both FL with WLR.
- Image intensity ratios will also be analyzed with repeated measures analysis of variance (RMANOVA) with timing, image, method (FL /WLR), and device (Zeiss/OnLume) as the repeated factors in the model.
- SBR for FL and WLR measurements will be plotted. Values to the right of the line will indicate that there is improved visualization with FL images and values to the left of the line will indicate that there is improved visualization with WLR images(Equal performance of FL versus WLR will be indicated by dashed line (slope = 1)].
- To further assess timing, Cohorts B1 and B2 will be compared. Image ratios will be averaged to get a single mean ratio per patient; then an unpaired t-test or Wilcoxon rank sum test will be used, as appropriate, separately for FL and WLR.

Paired t-tests will be used unless markedly non-normal data is observed including bimodal or other severe assumption violations; minor skewness is robust to the paired t-test and RMANOVA assumptions. If extreme skewness with outliers, or bimodal distributions are observed, then a Wilcoxon signed rank test will be used instead of a paired t-test and RMANOVA will be performed on the ranked data.

Similarly, unpaired t-tests will be used unless markedly non-normal data is observed including bimodal or other severe assumption violations; minor skewness is robust to the unpaired t-test assumptions. If extreme skewness with outliers, or bimodal distributions are observed, then a Wilcoxon rank sum test will be used instead.

The optimal cut-off points of SBR and the ability to detect the nerve will be studied using ROC (Receiver Operating Characteristics) curves analyses through logistic regression. In the logistic regression the outcome variable will be the categorized surgeon rating scale 1 : I do not see the nerve versus 4 to 5 : the nerve is visible. The Youden J index given by  $J = \text{Sensitivity} - (1 - \text{Specificity})$  will be used to select the optimal predicted probability cut-off. It is the maximum vertical distance between ROC curve and diagonal line. This will allow to maximize the difference between True Positive and False Positive. All possible SBR values and the corresponding sensitivity and specificity will be obtained using proc logistic in SAS [1]. The optimal cut-off will be determined overall and by device and individual Cohorts (i.e., Cohorts: A, A1, A2, A3, A4, A5, A6, B, B1, B2).

Image intensity ratios will be plotted against nerve diameter, with ratios on the y-axis and diameters on the x-axis. Plots will be displayed overall and by device and individual Cohorts (i.e., Cohorts: A, A1, A2, A3, A4, A5, A6, B, B1, B2).

QMS Document Name: Statistical Analysis Plan	Page 19 of 29
QMS No (include version ref): STF-015-GL.02	Document date: 09JUL2019
CONFIDENTIAL	

Image intensity ratios will be summarized separately for images with and without overlying tissue, overall and by device and individual Cohorts (i.e., Cohorts: A, A1, A2, A3, A4, A5, A6, B, B1, B2).

In the subset of images with overlying non-nerve tissue, depth will be measured via the amount of overlying tissue that there can be to still maintain the ratio of nerve to non-nerves. Depth will be summarized overall and by device and individual Cohorts (i.e., Cohorts: A, A1, A2, A3, A4, A5, A6, B, B1, B2).

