#### **4.1 Sample Size Estimation**

The primary objective of this study is to evaluate the safety of ALM-488 administered by intravenous (IV) infusion to subjects undergoing head and neck surgery.

At each dose level, a cohort of 3 subjects will be enrolled for safety and tolerability evaluation. If there are no subjects with a DLT at a given dose level, new subjects will be enrolled at the next dose escalation level. If there are  $\geq 1$  subjects having any DLT, the enrollment to that specific dose and dose escalation will stop. New subjects will be enrolled at the next dose de-escalation level. There will be a minimum of 3 cohorts. Given that there will be 3-6 subjects for each dose level, 9-36 subjects will be needed for the dose escalation/de-escalation cohorts.

It is anticipated that the proposed dose range (100-1000mg) is expected to yield optimal imaging performance, with an initial starting dose of 100mg that has been selected based on supportive nonclinical testing. If the 100 mg dose is found to provide adequate fluorescence imaging of nerves, a dose de-escalation schedule will be followed to ensure that the lowest effective dose is determined. If imaging at starting first de-escalated dose (75 mg) becomes less adequate compared to 100mg as determined by the SRC, then imaging at dose escalation schedule will resume - beginning at 200mg. The Optimal Dose will be determined by the SRC as the lowest possible dose and toxicity profile that achieves adequate imaging performance of nerves using WLR combined with FL.

The Dose Timing Cohort will use the Optimal Dose as defined by the SRC following completion of the Dose Escalation/De-Escalation cohorts. Subjects in the Dose Timing phase will be administered ALM-488 at two planned operative times before surgery to assess the impact of timing of administration on fluorescence image quality. This phase will consist of 2 cohorts, 6 subjects/cohort: (1) dose administration 3-5 hours in advance of surgery, (2) dose administration 1-3 hours in advance of surgery. A total of 12 subjects will be needed for the Dose Timing phase.

In summary, 9-36 subjects may be enrolled into the dose escalation/dose de-escalation cohorts and 12 subjects may be enrolled into the dose timing cohort. A total of 21-48 subjects may be enrolled into this study.

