In listings, data will be sorted by dose Cohort, site, and subject ID, and when appropriate by image, visit or other identifiers for sequence or type of observation.

Factor 365.2425 is used for duration conversions between days and years. Factor 30.436875 is used for duration conversions between days and months.

If not otherwise specified, all statistical tests will be two-sided, and confidence intervals will be two-sided and will be at the 95% confidence level.

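### In dose cohorts of 3 to 5 the signed-rank fallback for fluorescence (FL) against white light (WLR) cannot reach two-sided p<0.05 in its exact form, and its trigger cannot be judged from three values

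*SAP*

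**What the plan says.** SAP section 13.1 first reduces the image data: "For each Cohort, SBR will be averaged to get a single mean ratio per patient". The test of the two imaging methods within each cohort is given in these terms: "then a paired t-test or Wilcoxon signed rank test will be used, as appropriate, to compare SBR between FL and WLR". The t-test is the default: "Paired t-tests will be used unless markedly non-normal data is observed including bimodal or other severe assumption violations". The fallback is stated as: "If extreme skewness with outliers, or bimodal distributions are observed, then a Wilcoxon signed rank test will be used instead of a paired t-test".

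On cohort size, SAP section 4.1 says: "At each dose level, a cohort of 3 subjects will be enrolled for safety and tolerability evaluation". The same section allows 3 to 6 subjects per dose level and at least 3 cohorts; section 4 allows up to 6 cohorts. Each timing cohort, B1 and B2, has 6 subjects. The efficacy set in section 5 requires at least one evaluable image, so the number analysed can be below the number enrolled.

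Section 8.1 says "all statistical tests will be two-sided, and confidence intervals will be two-sided and will be at the 95% confidence level", and has p-values printed to at least four decimals. The text supplied gives no significance level, and no effect size, SD or power for this comparison.

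**The concern.** A rank test on very few pairs has few possible outcomes, and so a floor under its p-value. If the floor lies above the level at which readers judge significance, the result is fixed before any data are seen. Here the plan moves from a test that can reach that level to one that cannot, on a distributional judgement that three numbers cannot support. The study is open label, so the choice would be made with the FL and WLR results in view.

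What is at stake is how the per-dose results are read. Section 13.1 lists SBR among the endpoints assessed during enrolment to settle the dose for the timing cohorts. A printed p of 0.2500 for a dose at which every patient favoured FL looks like absence of effect, when it is the strongest result that the test can give.

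**Working it through.** **Inputs.** n = 3 to 6 per dose cohort, 3 to 6 dose cohorts, 6 per timing cohort (SAP sections 4 and 4.1); one mean per patient and method (13.1); two-sided tests and 95% intervals (8.1). Assumed: threshold 0.05, to match the 95% level. The SD of the per-patient FL minus WLR difference is not given, so effects are in units of that SD.

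**The plan's own figures.** 3 × 3 = 9 and 6 × 6 = 36 dose-cohort subjects; 2 × 6 = 12 timing subjects; totals 9 + 12 = 21 and 36 + 12 = 48. These agree with section 4.1. They are head counts, not a power calculation.

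**Floor of the signed-rank test.** With n non-zero, untied differences there are 2^n equally likely sign patterns under the null. The most extreme result is all signs alike, so the smallest two-sided p is 2/2^n.

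| n | Exact | Normal approx. | With continuity correction | t approx. |
|---|---|---|---|---|
| 3 | 0.25 | 0.109 | 0.181 | 0.074 |
| 4 | 0.125 | 0.068 | 0.100 | 0.030 |
| 5 | 0.0625 | 0.043 | 0.059 | 0.013 |
| 6 | 0.031 | 0.028 | 0.036 | 0.006 |

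At n=3 no version reaches 0.05. At n=4 and n=5 the exact test does not; some approximations do, but large-sample approximations are not credible at that size. Section 13.1 does not say which version is meant. At n=6 the exact test reaches 0.031 only if all six differences have the same sign.

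**Can the trigger be assessed?** With three values the sample skewness coefficient cannot exceed √3 = 1.73, and no value can lie more than 2/√3 = 1.155 SD from the mean. Two values close together and one apart is a common pattern in any sample of three, so it cannot identify bimodality or an outlier.

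**Does the choice matter?** Illustrative differences of 0.9, 1.0 and 1.1: mean 1.0, SD 0.1, t = 1.0/(0.1/√3) = 17.3 on 2 df, p = 0.0033. The exact signed-rank p for the same data is 0.25.

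**Default t-test at n=3.** Half-width of the 95% CI = t(0.975; 2 df)/√3 = 4.303/1.732 = 2.48 SD; the observed mean difference must exceed this for p<0.05. Power from the non-central t:

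| True difference (SD) | 1 | 2 | 3 | 4 |
|---|---|---|---|---|
| Power, n=3 | 18% | 47% | 75% | 91% |

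80% power needs a difference of 3.26 SD. At n=6 it needs 1.43 SD.

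**One residual variance across cohorts of 3, if SDs are equal.**

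| Cohorts completed | df | Half-width (SD) | Power at 2 SD |
|---|---|---|---|
| 1 | 2 | 4.303/√3 = 2.48 | 47% |
| 2 | 4 | 2.776/√3 = 1.60 | 74% |
| 3 | 6 | 2.447/√3 = 1.41 | 82% |
| 6 | 12 | 2.179/√3 = 1.26 | 89% |

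**If SDs are not equal.** Simulation with three cohorts of 3: for SD ratios 1:1.5:2 the nominal 95% pooled intervals cover 99%, 95% and 89%; for 1:2:3, coverage in the highest-SD cohort is 85%. The ratios are assumptions.

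**The case against.** **A reader might infer that these tests set the dose.** They do not. Section 13.1 says that the endpoints are assessed for that purpose. The Safety Review Committee sets the dose on safety and adequacy of fluorescence (section 4), and section 12 asks for no DLTs and adequate nerve signal against background. No p-value enters any dose rule, and no interim analysis is planned. This stands and limits the harm to interpretation.

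**A reader might also infer that the t-test at n=3 is nearly useless.** That goes too far. It can reach significance when gains are consistent, and has 91% power at 4 SD. The documents give no SD, so nobody can say where on that range the trial lies. Imprecise is the right word.

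**If non-normality cannot be seen in three values, the default should stand and the fallback will rarely be used.** This is fair as to frequency. But the rule is written, has no workable criterion, and leaves the analyst free to invoke it after seeing the data.

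**Other analyses may cover the gap.** A pooled Cohort A comparison (9 to 36 subjects) would not have this floor, and B1 and B2 with six each can reach 0.031. However, the test is specified separately for each cohort. The RMANOVA names timing, image, method and device but not dose, so as written it gives no FL–WLR estimate by dose.

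**Early efficacy is exploratory here and safety is the primary objective.** True. It lowers the weight of the point but does not make an unattainable test informative.

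**Conclusion.** The point holds as a defect in how the per-cohort FL against WLR evidence would be tested and read. The exact signed-rank fallback cannot give two-sided p<0.05 at n=3, 4 or 5, and the condition for using it cannot be assessed at n=3. That part is arithmetic and rests only on the cohort sizes, the exact form of the test and the assumed 0.05 threshold. The imprecision of the t-test at n=3 is certain in SD units; its practical size depends on an SD that the documents do not give. A non-significant result in a three-subject cohort is not evidence that FL is no better than WLR at that dose. The documents do not support going further, to say that a wrong dose would follow. The change is worth making before the analysis, but it does not threaten the primary safety objective.

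**What to change.** In SAP section 13.1:

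1. For cohorts of 3 to 5, remove the data-driven choice of test. Report the mean per-patient FL minus WLR difference for each dose with its t-based 95% CI, and list the individual differences.
2. Use the signed-rank test only where n is at least 6, or pooled over Cohort A, as a sensitivity analysis, and state that it is exact.
3. Add as support one linear model on the per-patient FL minus WLR difference, with dose cohort as a factor and a common residual variance. Show the separate-variance intervals beside it.
4. State the significance level if p-values are kept, and say that a non-significant result in a small cohort is not evidence of no difference.

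The cost is one SAP paragraph and one program, with no extra patients. The pooled model should not be the only analysis. If the SD rises with dose, its intervals under-cover in the most variable cohort (about 85 to 89% in the cases above). Its gain in precision also arrives only after several cohorts are complete, so the first cohort still rests on 2 df.
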